12.2. Review and Approval of Trial Protocol

The trial protocol should be internally approved and filed according to the company's SOP prior to submitting to the external agency (including but not limited to the government regulatory agencies, Ethics Committee).

The clinical trial protocol should not be implemented until the written approval is obtained from the Ethics Committee according to the relevant requirements of laws and regulations.

12.3. Process of Informed Consent and Text of Informed Consent Form

12.3.1. Process of Informed Consent

The informed consent of all potential patients must be obtained prior to performing any study tests/procedures that are not SOC. Once the investigator determines that the patients are suitable for participating in this study, the investigator must explain the background of the study presented and the benefits and risks of surgery and study to the patients and answer the questions raised by patients. Only the patient who signs the informed consent form that is approved by the EC prior to participating in the study is eligible to participate in this study.

Each patient (or legally authorized representative) must sign and date the informed consent form that is approved by the EC (and other documents as per local regulations) prior to implementing any study-related items or operations not belonging to the SOC and after the nature of this study is fully explained.

The process of obtaining the written informed consent needs to prove that the subjects volunteer to participate in this study. All aspects of this study must be clarified to the subjects prior to signing the informed consent form. The process of obtaining the informed consent must be clearly documented by the investigator and/or designated person in the original clinical trial documents of subjects. The investigator has responsibilities to ensure the process of obtaining the informed consent is implemented according to the Good Clinical Practice for Medical Device Trials and related regulations, such as ISO 14155, the Declaration of Helsinki.

12.3.2. Text of Informed Consent Form

See the attached ICF.

13. DEVICE MANAGEMENT

In this study, the sponsor will supply all study products. All devices clearly labeled as "For Study Only" on the packaging must be stored according to the product labeling and IFU conditions. It is the responsibility of the Principal Investigator to ensure that devices are stored correctly at the sites.

The Principal Investigator or responsible person designated by the Principal Investigator must account for all study devices throughout and, at the end of, the clinical study. During the entire course of the study, the study ablation probes must be stored in a locked or secure access location. An inventory record must be maintained of all devices received, used or returned during the clinical trial. Details of the product code and lot numbers must be documented in the CRF as well as the patient's hospital notes. The Principal Investigator must allow the Monitor access to the secure facility where the study devices are stored during the clinical trial to check inventory. At the end of the clinical trial all machine and all unused probes must be returned to Johnson & Johnson Medical (Shanghai) Ltd. with the appropriate study device return form.

13.1. Packaging and Labeling of Study Device

All study devices provided by the sponsor in this study will be prepared, packaged, and labeled under the responsibility of qualified personnel or sponsor's designee in accordance with the company's SOPs, Good Manufacturing Practice (GMP) guidelines, and applicable local laws/regulations.

Each device is labeled in accordance with regulatory agency guidelines, GMPs, local laws and regulations, and company SOPs to identify investigational product for clinical trial use only.

13.2. Shipping of Study Device

The sponsor or sponsor's designee will ship the device to the study site under the device shipping conditions specified in the device's instructions.

13.3. Management of Study Device

The sponsor will be responsible for supplying qualified study products to the site. Each site will designate study personnel to be responsible for the management of the study device. During the entire course of the study, the study ablation probes must be stored in a locked or secure access location. The investigator should ensure that all investigational medical devices are only used for the subjects of the clinical trial. Details of the product code and lot numbers must be documented in the CRF as well as the patient's hospital record.

Records related to the receipt, distribution, use, recovery and disposal of investigational products shall be maintained in accordance with GCP requirements. Upon receipt of the investigational product at the site, the investigational product must be reconciled and packaged in the correct quantity and under the appropriate shipping conditions. During the study, a designated person will be responsible for recording and counting the use of the study product.

The Principal Investigator must allow the Monitor access to the secure facility where the study devices are stored during the clinical trial to check inventory. The responsible monitor will review the investigational device accountability as applicable. At the end of the clinical trial all machine and all unused study devices must be returned to Johnson & Johnson Medical (Shanghai) Ltd. with the appropriate study device return form.

13.4. Return and Destruction of Study Device

All machine, unused, opened, unused, damaged, mislabeled, or malfunctioning study devices will be returned to the Sponsor's designated address. Complete the appropriate form to properly return the device to the sponsor's specified address.

14. REGULATIONS OF ADVERSE EVENT AND DEVICE COMPLAINT REPORTING

14.1. Adverse events

An adverse event refers to any detrimental medical events in the course of a clinical trial, whether or not related to the investigational medical device.

From the time of signing the informed consent form until approximately 30 days (Visit 3) after ablation (including primary and repeat ablation) or early discontinuation, all adverse events will be recorded. During this period, all adverse events from the start of ablation (i.e., probe puncture on the skin) will be reported.

After approximately 30 days (Visit 3) post ablation, adverse events considered by the investigator as related to the study device or/and study procedures and all serious adverse events will be recorded and reported till the end of the study or early discontinuation.

The investigator will determine whether AEs have occurred and determine the relationship of these events to the study device or ablation procedure at each evaluation for subjects enrolled in the clinical study.

All AEs must be recorded in the original records and entered in the e-CRF. All AEs need to be recorded in the Electronic Data Capture (EDC) system (also called study database) within 2 weeks of site awareness.

The following guideline should be used to determine the severity of each AE:

AE severity grading criteria:

Mild	Awareness of sign or symptom that does not interfere with the subject's usual activity or is transient, resolved without treatment and with no sequelae
Moderate	Interferes, but does not hinder, the subject's usual activity and may require treatment
Severe	Symptoms causing severe discomfort, substantial impact on subject's usual activities, treatment or intervention required

The AEs should be classified according to the SIR classifications:

Category	Definitions
Mild complications	

A	No intervention, no adverse consequences
B	Nominal treatment, no adverse consequences; including stay for observation
Severe complications	
C	Treatment required, short-term hospitalization (< 48 hours)
D	Severe treatment required, increased need for care level, prolonged hospitalization (> 48 hours)
E	Permanent adverse sequelae
F	Dead

It is the investigator's responsibility to assess the relationship between all AEs and the study procedure. The following guidelines should be used in determining the relationship of an AE to a device, study procedure, or other causality:

Not Related:	
Relationship to the procedure or device can be excluded when:
 
 • The event is not a known side effect of the product category the device belongs to or of similar device and procedures; • The event has no temporal relationship with the use of the device or the procedures; • The event does not follow a known response pattern to the device (if the response pattern is previously known) and is biologically implausible; • The discontinuation of the device application or the reduction of the level activation/exposure (when clinically feasible) and reintroduction of its use (or increase of the level of activation/exposure), does not impact on the event; • The event involves a body-site or an organ not expected to be affected by the device or the procedure; • The event can be attributed to another cause (e.g. an underlying or concurrent illness/clinical condition, an effect of another device, drug, treatment, or other risk factors); • Harms to the subject are not clearly due to use error; or
--------------	---

	
 • To establish the non-relatedness, not all the criteria listed above might be met at the same time, depending on the type of device/procedure and the event.
Unlikely	The relationship with the use of the device seems not relevant and/or the event can be reasonably explained by another cause, but additional information may be obtained.
Possible	The relationship with the use of the device is weak but cannot be ruled out completely. Alternative causes are also possible (e.g. an underlying or concurrent illness/condition and/or an effect of another device, drug, or treatment). Cases where relatedness cannot be assessed, or no information has been obtained should also be classified as possible.
Probable	The relationship with the use of the device seems relevant and/or the event cannot reasonably be explained by another cause, but additional information may be obtained.
Causal Relationship	
The event is associated with the device or with procedures beyond reasonable doubt when:
 
 • The event is a known side effect of the product category the device belongs to or of similar device and procedure; • The event has a temporal relationship with the device uses/application or procedures • The event involves a body-site or organ that: 
 ◦ The device or procedures are applied to ◦ The device or procedures have an effect on • The event follows a known response pattern to the medical device (if the response pattern is previously known)

	
• The discontinuation of medical device application (or reduction of the level of activation/exposure) and reintroduction of its use (or increase of the level of activation/exposure), impact on the event (when clinically feasible)• Other possible causes (e.g. an underlying or concurrent illness/clinical condition and/or an effect of another device, drug, or treatment) have been adequately ruled out;• Harm to the subject is due to error in use• To establish the relatedness, not all the criteria listed above might be met at the same time, depending on the type of device/procedure and the event.
--	--

14.2. Serious Adverse Event

It is the investigator's responsibility to determine the "seriousness" of an AE using the protocol defined terms below. All SAEs need to be recorded in the Electronic Data Capture (EDC) system (also called study database) within 24 hours of site awareness. An SAE is an AE that results in one or more of the following for this study:

- Resulted in death: An AE that resulted in the patient's death.
- Life-threatening illness or injury: The patient is at imminent risk of dying at the time of the AE.
- Permanent Impairment: An AE that resulted in permanent impairment of a body function or permanent damage to a body structure.
- Required in-patient or prolonged hospitalization. Note: If a patient has prolonged hospitalization due to having an additional ablative procedure and with no other adverse event, this should not be considered an SAE.
- Resulted in medical or surgical intervention to prevent life threatening illness or injury or permanent impairment to a body or body function.
- Led to fetal distress, fetal death or congenital abnormality or birth defects.
- A persistent or significant disability or incapacity.

Notes:

1. Progression of the disease under investigation should not be reported as an SAE.
2. "Death" should not be reported as an SAE. The cause of death, however, should be reported as an SAE, except for progressive disease.
3. Planned hospitalization for a pre-existing condition, but without serious deterioration in

health, is not considered a serious adverse event.

4. A procedure required by the protocol is not considered an SAE unless the patient experiences a serious deterioration in health or hospitalization is prolonged.

14.3. Device Complaints

A device complaint is any written, electronic, or oral communication that alleges deficiencies related to the identity, quality, durability, reliability, safety, effectiveness, or performance of a product after it is released for distribution. Any device complaint must be notified to the monitor by the study site and tracked and reported according to the procedures specified by the sponsor. The monitor will track and report in time according to the methods specified by the sponsor and Chinese regulations and return relevant products (as required) to the quality department of JJMS/Johnson & Johnson Medical (China) Ltd. (JJMC) according to the sponsor's requirements.

14.4. Device Deficiencies

Device defects refer to unreasonable risks that may endanger human health and life safety during medical use in the process of clinical trials, such as label errors, quality issues, and malfunction.

For equipment defects that may result in SAE, the sponsor shall report to the food and drug regulatory authority for registration and the health and family planning department at the same level within 5 working days after the knowledge. Meanwhile, it shall notify other clinical trial institutions and investigators participating in the trial and promptly advise the ethics committees of relevant clinical trial institutions via its medical device clinical trial management department. The investigator should record all AEs occurring and device deficiencies found in the process of clinical trial, work with the Sponsor to analyze the causes of the events, generate the written analysis report, present the comments on the continuation, discontinuation or termination of the trial, and report to the Ethics Committee by the administrative department for clinical trial of medical device of clinical trial institution for review.

14.5. Reporting Procedure, Contact Person Information

The investigator should provide the sufficient treatment for any AE of any subjects, including the laboratory detection value with clinical significance whether or not it is related to this study.

From signing the ICF, all AEs related to the patient's participation in this study should be followed up until the event is resolved, or if the event causes the permanent damage, it should be followed up until the event is stable and the clinical outcome is determined. If the event is not resolved or stable at the end of study, the medical monitor in this clinical study will decide whether it is necessary to collect further follow-up information.

All AEs and SAEs that occur within the period from Visit 2A (day of ablation) to Visit 3 (about one month after ablation) will be reported; from Visit 3 to through the end of the study, all SAEs, and AEs assessed as related to the study device/ablation procedure by the investigator will be reported. All AEs should be followed up, until the AE is resolved, stable or the study is completed.

The investigator should record the nature, severity, treatment and outcome of an SAE, and determine whether it is related to the study device or ablation procedure. The investigator will report all AEs to the Sponsor via the study database EDC.

The investigator must submit any SAEs that occurred in the study and the device deficiencies that may cause an SAE, to the Sponsor and National Medical Products Administration (NMPA) (or designated person) immediately after being informed of the event. If required by the Sponsor, the further information should be provided.

The investigator and Sponsor should report the SAEs which occurred in the study, and the device deficiencies that may cause an SAE, to the regulatory authorities at every level according to the requirements of laws and regulations.

For all SAEs and device deficiencies that may cause SAEs, the Sponsor should report to the Food and Drug Administration where the clinical study was filed and the competent department of health and Family Planning Commission within 5 workdays after awareness. The Sponsor should also inform other clinical trial institutions/sites and investigators that participate in the trial and inform the Ethics Committees by their medical device clinical trial management departments in a timely manner.

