3.2. Contents of Clinical Trial

This study employs single-arm, prospective and multi-center design with single-arm performance goal comparing study device performance indexes with the predetermined performance goal, in order to evaluate study device efficacy and safety. Approximately 120 plus run-in subjects (each site will enroll 2 run-in subjects) of Chinese patients with non-small cell lung cancer or oligometastatic lung tumor scheduled for microwave ablation will be recruited. After the informed consent is signed, lung cancer patients according to the inclusion and exclusion criteria will be included in this study. All qualified subjects at the study sites will receive the same procedure: microwave ablation using only the NeuWave Certus Microwave Ablation System and accessories. Subjects in this study will come to their study site for the ablation procedure. After the ablation procedure, the patient will be observed according to medical routine, and afterwards may return home. If the Study Doctor decides it is warranted for patient safety, the patient will remain in the hospital longer. All subjects will be required to return to their study site for at least 4 follow-up visits over a period of 12 months to assess the efficacy and safety of ablation.

Computerized tomography (CT) is used to evaluate the efficacy to verify whether patient's lung tumor is completely ablated. CT scan will be carried out approximately 10 minutes after the ablation to assess Technical Success Rate and A0 Ablation Rate. Enhanced CT scan will be completed within 30 days (± 7 days) after the ablation to evaluate Technical Efficacy Rate. During the subsequent visits in Months 3, 6, and 12 after the ablation, subjects will receive at least one enhanced CT scan each time at the study site to observe whether there are imaging manifestations of tumor progression inside the ablation zone and at its margin. These enhanced CT scans will serve as the basis for determining the Local Tumor Progression. Progression-Free Survival including local, regional, or distant progression will also be determined according to the study physician and/or the patient's treating oncologist. Another valuable endpoint during the 12-month follow-up period will be overall survival.

Within 30 days after the ablation (initial or repeated), all adverse events (AE) and serious adverse events (SAE) experienced by the patient will be evaluated; from 30 days after the ablation to the

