For efficacy parameters including Technical Efficacy, Technical Success, A0 Ablation, Re-Ablation Technical Success and Local Tumor Progression, IRC will be used to evaluate the CT images in order to achieve standardization and consistency defined in the protocol and to reduce biases in surgeon's judgment. Investigator's evaluation results will also be recorded. Both results will be recorded in the e-CRF. The composition of IRC and endpoint definition details will be described thoroughly in a separate imaging chapter, which will be finalized before the first patient is enrolled. Primary statistical analysis and hypothesis testing for the primary effectiveness endpoint will be based on IRC's evaluation results.

For effectiveness endpoints Progression-Free Survival and Overall Survival, they will be based on reports by study physician and/or subject's treating oncologist. The evaluation results will be recorded in the e-CRF and reported in the final clinical study report.

- Primary efficacy endpoint:
 - Technical Efficacy Rate will be determined according to lung enhanced CT at Visit 3 (30 days±7 days after surgery).
- Secondary efficacy endpoints:
 - Technical Success Rate, A0 Ablation Rate, and Re-ablation Technical Success Rate: determined according to the maximum diameter, minimum diameter and minimal ablative margin of the ablated lesions as measured by lung CT approximately 10 minutes after ablation.
 - Local Tumor Progression: determined by lung enhanced CT after initial ablation.
 - Progression-Free Survival will be determined by study physician and/ or be reported by the patient's oncologist after initial ablation.
 - Overall Survival will be determined based on investigator recorded ablation time and death time.

See Section 8 for analytical methods of the above endpoints.

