7.1.8. Safety Evaluation Method

1) Description of safety parameters

Safety parameters include:

- All AEs from the start of any ablation procedure (from the probe puncture on skin) to 30 days post-ablation or early discontinuation.
- All SAEs from the start of ablation procedure through the end of the study or early discontinuation.
- All device-related AEs, procedure-related AEs, device-related SAEs and procedure-related SAEs from the start of ablation procedure through the end of the study or early discontinuation.

The incidence of the prespecified AEs below will also be summarized and reported:

1. Pneumothorax (all and those requiring chest tube drainage)
2. Hemorrhage (all and those requiring treatment)
3. Post-ablation syndrome
4. Chest wall pain
5. Pleural effusion (all and those requiring chest tube drainage)
6. Pneumonia
7. Lung or chest abscess
8. Other infections
9. Bronchopleural fistula

2) Selection of method and time to evaluate, record, and analyze the safety parameters

From the time of signing the informed consent form until approximately 30 days (Visit 3) after ablation (including primary and repeat ablation) or early discontinuation, all adverse events will be recorded. During this period, all adverse events from the start of ablation (i.e., probe puncture on the skin) will be reported.

After approximately 30 days (Visit 3) post ablation, adverse events considered by the investigator as related to the study device or/and study procedures and all serious adverse events will be recorded and reported till the end of the study or early discontinuation.

For subjects who stop ablation and withdraw from the study without ablation power emission while the needle has punctured the skin during the ablation procedure, the subject will be followed up for safety events up to 30 days after the procedure. If the discontinued subject reports a serious adverse event, the subject will be followed until event resolution, stabilization, or until the event is adequately explained.

The safety parameters will be recorded on the e-CRF according to the investigator's record, medical record, and all other related source documents collected at each follow-up visit.

See Section 8 for safety endpoint analysis methods.

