- Relevant concomitant medication: including antineoplastic agents such as chemotherapy/targeted therapy/immunotherapy and drugs related to the recorded adverse events.
- Concomitant procedure: the name, time, site and purpose of the concomitant operation (including but not limited to puncture, radiotherapy, ablation therapy and surgical resection).
- All AEs considered by the investigator as related to the study device or/and study procedures and all SAEs.

5) Unscheduled Visits

The following data will be collected at all unscheduled visits:

- Reason for the unscheduled visit.
- Relevant concomitant medication: Including antineoplastic agents such as chemotherapy/targeted therapy/immunotherapy and drugs related to the recorded adverse events.
- Concomitant procedure: the name, time, site and purpose of the concomitant operation (including but not limited to puncture, radiotherapy, ablation therapy and surgical resection).
- All AEs and SAEs.
- Any other study assessments, per SOC.

Notes: Re-ablations on the target tumor(s) in the study should only be conducted after finishing Visit 3 evaluation.

Re-ablations using the microwave ablation system and ablation probe provided in this study can only be performed when there is local progression of lung tumor after initial ablation, or residual tumor or insufficient margin during initial ablation of tumor (if considered medically indicated/necessary by the investigator so as to obtain sufficient ablation margin of tumor). The study device provided by this study cannot be used for the ablation of other lesion foci.

For each re-ablation using the study device within this study, the following information will be captured:

- Reason for the re-ablation.

- Record ablation procedure details, including but not limited to the following:
 - Procedure date and time
 - Mode of anesthesia
 - Guidance method used
 - Anatomic location of ablated tumor
 - Number of ablation cycles
 - Ablation power and time
- Device count: all probe types and amounts.
- Document the investigator's re-ablation result evaluation.
- Submit the CT to IRC for re-ablation result evaluation.
- All AEs and SAEs.

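### Protocol 14.5 lets all-AE reporting stop at Visit 3, as early as day 23, while the safety endpoint runs to day 30, so the descriptive 30-day all-AE figures can be understated

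*Protocol*

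**What the plan says.** The safety endpoint in Protocol 7.1.8 is "All AEs from the start of any ablation procedure (from the probe puncture on skin) to 30 days post-ablation or early discontinuation". The synopsis and SAP 1.3.2 define it the same way. Protocol 3.2 also uses a fixed window, with no mention of a visit: "Within 30 days after the ablation (initial or repeated), all adverse events (AE) and serious adverse events (SAE) experienced by the patient will be" evaluated.

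The collection rules are tied to Visit 3 instead. Protocol 14.5 asks for "All AEs and SAEs that occur within the period from Visit 2A (day of ablation) to Visit 3" and then narrows the scope: "from Visit 3 to through the end of the study, all SAEs, and AEs assessed as related to the study device/ablation procedure by the investigator" are reported. Protocol 14.1 merges the two time points: "until approximately 30 days (Visit 3) after ablation (including primary and repeat ablation) or early discontinuation, all adverse events will be recorded". The synopsis, note 22 to Table 1 and the second part of 7.1.8 have the same merged rule.

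Visit 3 has a window. Protocol 7.1.6 refers to the "lung enhanced CT at Visit 3 (30 days±7 days after surgery"), and Table 1 gives the same interval. At Visits 4 to 6, Protocol 7.2.3 lists only this for AE collection: "All AEs considered by the investigator as related to the study device or/and study procedures and all SAEs".

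SAP 8.10.7 plans a summary of all AEs and SAEs in the first 30 days after the initial ablation. It reports numbers of events and numbers and percentages of subjects, without adjustment for length of observation.

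**The concern.** The endpoint is fixed in days, but the collection rule in 14.5 is fixed to a visit that can fall a week earlier. A subject seen on day 23 is fully compliant, yet from then on a non-serious AE must be reported only if the investigator judges it related. That subject still counts in full in the denominator of the 30-day table.

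Protocol 3.2 says the safety result within 30 days of ablation goes to the NMPA with the efficacy result. In a single-arm, open-label trial, the all-AE table is the safety summary that does not depend on the investigator's view of causality. During the gap that independence is lost. The prespecified list includes pneumonia and other infections, where attribution may be uncertain.

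**Working it through.** The plan states no figure for this point, so there is none to reproduce. The check is date arithmetic plus a comparison of sections.

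**Inputs**
- Visit 3 window: day 30 ± 7 (Protocol Table 1 and 7.1.6).
- Endpoint window: probe puncture to day 30 (Protocol 7.1.8, SAP 1.3.2).
- End of all-AE reporting: Visit 3 (Protocol 14.5).
- Scope after Visit 3: SAEs and related AEs (Protocol 14.5; Visits 4 to 6 in 7.2.3).

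**Step 1: range of Visit 3.** Earliest 30 − 7 = day 23; latest 30 + 7 = day 37.

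**Step 2: uncovered days.** For a Visit 3 on day v, gap(v) = max(0, 30 − v).
- v = 23: gap = 7 days (days 24 to 30), 7/30 = 23.3% of the window.
- v = 27: gap = 3 days, 3/30 = 10%.
- v = 30 or v = 37: gap = 0.

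**Step 3: does a later scheduled contact recover these days?** No. Visits 4 to 6 ask for related AEs and SAEs only. An unscheduled visit collects all AEs (Protocol 7.2.3), but none is required.

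**Step 4: direction.** For late attenders, all AEs are collected up to day 37, but the 30-day table stops at day 30, so days 31 to 37 cannot offset what is missing for early attenders. Any error is downward.

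**Step 5: what can be lost.** An event is missed only if all four conditions hold: it is non-serious; it is judged not related; it starts between an early Visit 3 and day 30; and it is not seen at an unscheduled visit. SAP 8.10.7 counts Unlikely as related in its main definition. The protocol does not say whether its reporting rule does. The lost class is therefore either Not Related events alone or Not Related plus Unlikely.

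**Step 6: repeat ablation.** Protocol 7.1.8 and 14.1 include AEs after a repeat ablation. The all-AE sentence in 14.5 runs from Visit 2A to Visit 3 and does not mention repeats. Protocol 7.2.3 says re-ablation should follow the Visit 3 evaluation, so a literal reading of 14.5 leaves the 30 days after a repeat under the restricted rule. That conflicts with the other two sections.

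**Check of the fix.** With collection to max(v, 30), the gap is 0 for every v from 23 to 37.

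**The case against.** The strongest reply is that the documents treat day 30 and Visit 3 as one nominal time point. The merged wording appears in four places, and in 7.1.8 it follows directly after the endpoint, so it can be read as the way the endpoint is put into practice. Protocol 3.2 gives a plain 30-day rule, and Protocol 14.4 and 21.2 tell the investigator to record all AEs that occur. On this view the defect is loose wording, and many sites would collect to day 30 anyway.

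Part of this stands: the documents do not establish that every site would stop on day 23. But nothing says which statement governs, nothing says whichever is later, and 14.5, the section on reporting procedure, settles on the visit. The Visit 4 to 6 lists follow the same rule.

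The reply is also right about scale. The summary is descriptive and has no success criterion. A subject with an AE before Visit 3 is already in the any-AE percentage; only the event count or a particular preferred-term row would be short.

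A reader might be tempted to turn the gap into a percentage of lost person-time and read that as the bias in the AE rate. The documents do not support this. They give no distribution of Visit 3 dates, and the planned summaries are counts and percentages of subjects, not person-time rates.

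**Conclusion.** The gap is real and minor. For subjects seen before day 30, non-serious AEs judged not related are not systematically collected for up to 7 of the 30 endpoint days. The descriptive 30-day all-AE counts and percentages can therefore be too low and cannot be too high for this reason.

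The 7-day maximum needs no assumption beyond the stated window and a literal reading of 14.5. The number of missed events cannot be computed, because the documents give neither AE rates nor attendance dates.

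A reader might infer that the whole 30-day safety result is unreliable. That does not follow: SAEs and device- or procedure-related AEs are required to the end of the study, so early attendance at Visit 3 does not shorten their collection. The primary effectiveness test is untouched.

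**What to change.** Reconcile the synopsis, Table 1 note 22 and Protocol 3.2, 7.1.8, 14.1 and 14.5, so that each says all AEs are collected to the later of Visit 3 and day 30 after any ablation, initial or repeat. For subjects whose Visit 3 falls before day 30, add a brief phone AE check at day 30 with a matching CRF prompt. The protocol already accepts a phone contact for the Visit 3 pain score.

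The check should not wait for Visit 4. Taking 3 months as 90 days, Visit 4 falls on days 76 to 104, so events from days 24 to 30 would be recalled after 76 − 30 = 46 to 104 − 24 = 80 days. The primary analysis also follows the 1-month visit (Protocol 8.1, SAP 8.13) and waits for Visit 4 only where the primary-endpoint imputation needs it. If the last subject attends early, the data cut would need to wait for that subject's day 30, at most 7 days.

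The cost is a wording amendment, one CRF prompt and one short call for early attenders.
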